Short Title	PATRC
Protocol Number	18-1789
Phase	Pilot
Methodology	Four-session, crossover design, active sham controlled
Study Duration	This study is expected to last eighteen months.
Study Center(s)	This is a four-session and single-site study performed at The University of North Carolina at Chapel Hill.
Objectives (Purpose)	The purpose of this pilot study is to modulate oscillatory activity in the prefrontal cortex using rhythmic transcranial magnetic stimulation during performance of a cognitive control task.
Number of Participants	100 (until 48 are completed)
Diagnosis and Main Inclusion Criteria	Eligible participants will be healthy adults between the ages of 18-35 with no history of mental or psychiatric disorder.
Description of Intervention (Procedures/methods)	The participants will perform a cognitive control task. During the task, rhythmic trains of transcranial magnetic stimulation will be delivered. Electroencephalography will be collected throughout every session.
Related IRB Applications	17-0149

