2.3.2 PRIMARY OUTCOME – SPECTRAL POWER

RATIONALE. The electrical activity of the brain is recorded during performance of the task and during brain stimulation. The investigators will perform Morelet wavelet convolution on the recorded electrical signal to calculate the spectral power of theta (5-8 hertz) and alpha (8-12 hertz). Theta oscillations are known to be generated in frontal cortex when cued to the contralateral visual field. Alpha oscillations are known to be generated in parietal cortex when cued to the ipsilateral visual field.

ALTERNATIVE HYPOTHESIS. When the frequency of TMS to either frontal or parietal cortex is compatible with the endogenous activity, spectral power in the stimulated frequency band should increase relative to TMS that is incompatible. Therefore, we will report the TMS compatibility effect as the average of "theta power for theta minus alpha TMS to frontal cortex for retro-cue right" and "alpha power for alpha minus

theta TMS to parietal cortex for retro-cue left". We will report the mean and standard deviation of the TMS compatibility effect across participants. This effect will be investigated using repeated-measures two-way ANOVA, and an interaction between TMS site and TMS frequency is hypothesized.

NULL HYPOTHESIS. There is no systematic effect of frequency specific TMS on spectral power.

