4 BASIC STUDY DESIGN

This study is a pilot, four-session study with TMS and EEG to understand the neural oscillatory basis of cognitive control. Participants will perform a cognitive control task in which a retro-cue is used to distinguish between relevant and irrelevant lateralized stimuli that need to be accurately recalled for testing in each trial. The rhythmic TMS manipulation targets the previously localized EEG frequencies and previously localized regions of the brain from MEG (Wallis et al., 2015). The frequencies of stimulation will be theta (5 hertz), alpha (10 hertz), and arrhythmic. The regions of stimulation will be anterior-MFG, inferior-IPS. The study consists of an initial screening session, a baseline session, and two counterbalanced stimulation sessions with TMS delivered during task performance. During the initial screening session, participants will learn and perform the cognitive control task at varying levels of difficulty in order to titrate their performance accuracy. During the baseline session, participants will perform the titrated cognitive control task while EEG is recorded. The motor threshold (MT) for each participant will also be calculated either on this day or during the Stimulation 1 session. MT is calculated by placing the TMS coil at a 45-degree angle from the midline along the central sulcus (just above the ears). An electrode is attached to the contralateral first dorsal interosseous muscle. Then the primary motor cortex is stimulated with single pulse TMS until a motor evoked potential (MEP) is generated in the contralateral hand muscle, defined as a near-instantaneous increase in electrical activity above 200 microvolts. Then the intensity of TMS is lowered until an MEP is evoked on five out of ten pulses. Additionally, visible hand twitches may be used as instead of visual twitches to determine MT. The MT allows for TMS to be calibrated to the particular sensitivity level of the individual participant's brain. On the subsequent TMS session we will stimulate at 110% of MT. We ensure that TMS is driving neural activity but that this activity is within the range of endogenous activity and hence is at an appropriately safety level according to guidelines established for TMS (Rossi et al. 2009). On the third and fourth session (Stimulation 1 and Stimulation 2) the anterior-MFG and inferior-IPS is targeted by rhythmic TMS during performance of the cognitive control task. The sequence of TMS targets will be randomized and counterbalanced across participants. However, it is not possible to double-blind the study because the location of the TMS coil needs to be aligned to the targeted brain region with neuro-navigation software (Localite, Sankt Augustin, Germany). In other words, the region targeted by TMS is necessarily visible to the experimenter for accurate targeting. The study will be single blinded as the participant will not know the anatomical differences between the targeted regions and the position on the scalp differs by only a few centimeters between each site. Critically, the manipulation of interest is the frequency of stimulation. On each trial, the frequency will be randomly selected, counter-balanced, and inter-mixed. The effects of rhythmic TMS do not last for more than a few cycles beyond stimulation itself (Thut et al. 2011; Hanslmayr et al. 2014; Albouy et al. 2017). Therefore, the experimental design randomly intermixes the frequency of stimulation within every task block. The critical analysis is the within participant comparison of frequency specific TMS effects for a single site. The sequence order of target sites will have no impact because all analyses will be run as a difference from our active control (arrhythmic TMS) from within the same session. In addition, a brief resting-state EEG recording will be collected at the beginning of the

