6.2 SPECIAL ASSAYS OR PROCEDURES

Each participant will receive stimulation on all four sessions, separated by a week. The baseline session will involve single pulse TMS for calculating the motor threshold. The other three sessions will involve train of rhythmic TMS during performance of a cognitive control task. For stimulation day, the rhythmic TMS trains are delivered on every trial of the task (there are 600 trials per session). Each train of TMS consists of 5 pulses. There will be a total of 2400 pulses delivered per session. Each TMS train will be separated by a minimum of 5 seconds. There are three possible trains: alpha frequency with a 100 milliseconds inter-pulse interval, theta frequency with a 200 milliseconds inter-pulse interval, and arrhythmic with a variable inter-pulse interval (not to exceed a minimum of 20 milliseconds inter-pulse interval). The inter-pulse interval, inter-train interval, number of trains, and TMS intensity are all under the safety guidelines set forth by Rossi et al. 2009 and is typical for experiments that deliver online TMS (Hanslmayr et al. 2014; Albouy et al. 2017).

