11.1 STATISTICAL ANALYSIS STRATEGIES

To control for non-specific effects of rhythmic TMS, we will use an active control: arrhythmic TMS (randomized inter-pulse-interval) that is matched to the target stimulation in number of pulses and temporal duration. All analyses will be run on the difference from condition-matched arrhythmic TMS. The key analysis is a two-way repeated-measures ANOVA with factors TMS frequency (theta vs alpha) and location (inferior-IPS vs anterior-MFG). Post-hoc t-tests will be run on a significant main effect of TMS frequency, TMS site, or interaction. We will use Tukey's adjusted significance for post-hoc testing to correct for multiple comparisons.

Primary outcome: working memory capacity. Two-way repeated-measures ANOVA run on the difference from arrhythmic TMS with factors (TMS site and TMS frequency). The direction of the retro-cue is held consistent for each site: for TMS to frontal cortex (anterior-MFG) the retro-cue to the right is used, and for TMS to parietal cortex (inferior-IPS) the retro-cue to the left is used. We hypothesize that theta frequency rhythmic TMS will improve behavioral performance when applied to anterior-MFG; i.e. a main effect of TMS frequency and/or an interaction between TMS frequency and cue. We hypothesize that alpha frequency rhythmic TMS will improve behavioral performance for retro-cue trials when applied to inferior-IPS; i.e. an interaction between TMS frequency and cue.

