Primary outcome: Spectral power. We collected EEG recording during the delivery of rhythmic TMS. We hypothesize, based on previous studies with identical rhythmic TMS trains, that rhythmic TMS will entrain neural oscillations in the targeted frequency. We will quantify entrainment from rhythmic TMS by analyzing the spectral decomposition of the EEG signal during TMS and immediately after TMS. We will run a six-cycle Morlet wavelet convolution with the EEG signal to estimate spectral density (microvolts per hertz). We hypothesize that the amplitude of theta activity will be increased following theta rhythmic TMS relative to theta activity following arrhythmic TMS. Similarly, alpha amplitude will be increased following alpha rhythmic TMS relative to alpha amplitude following arrhythmic TMS. The direction of the retro-cue is held consistent for each site: for TMS to frontal cortex (anterior-MFG) the retro-cue to the right is used, and for TMS to parietal cortex (inferior-IPS) the retro-cue to the left is used. We hypothesize an interaction between TMS frequency and cue.

Primary outcome: response time. Two-way repeated-measures ANOVA run on the difference from arrhythmic TMS with factors (TMS site and TMS frequency). The direction of the retro-cue is held consistent for each site: for TMS to frontal cortex (anterior-MFG) the retro-cue to the right is used, and for TMS to parietal cortex (inferior-IPS) the retro-cue to the left is used. We hypothesize that theta frequency rhythmic TMS will improve behavioral performance (decreased response time) when applied to anterior-MFG; i.e. a main effect of TMS frequency and/or an interaction between TMS frequency and cue. We hypothesize that alpha frequency rhythmic TMS will improve behavioral performance (decreased response time) for retro-cue trials when applied to inferior-IPS; i.e. an

interaction between TMS frequency and cue.

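### The spectral power analysis makes no stated use of each trial's own pre-train EEG power, a baseline already recorded that could sharpen the primary EEG contrasts at almost no cost

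*Combined protocol and SAP*

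**What the plan says.** For spectral power, a primary outcome, section 11.1 states: "We will quantify entrainment from rhythmic TMS by analyzing the spectral decomposition of the EEG signal during TMS and immediately after TMS". The spectral estimate is a six-cycle Morlet wavelet. The general rule in the same section is: "All analyses will be run on the difference from condition-matched arrhythmic TMS". Section 2.3.2 also defines a compatibility effect, which compares theta with alpha TMS at each site in the band of interest. Every comparison is therefore between sets of trials. No section names a pre-train window, a baseline correction, a normalisation or a trial-level covariate.

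The ingredients for one are present:

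- Study Summary: "Electroencephalography will be collected throughout every session". Section 2.3.2 adds: "The electrical activity of the brain is recorded during performance of the task and during brain stimulation". Appendix A schedules task EEG in both stimulation sessions.
- Section 6.2: "Each TMS train will be separated by a minimum of 5 seconds".
- Section 4: "On each trial, the frequency will be randomly selected, counter-balanced, and inter-mixed". Section 4 also says that effects of rhythmic TMS fade within a few cycles.

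Resting-state EEG is recorded at the start of the baseline and stimulation sessions, but that is one value per session and has no stated role in the analysis.

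**The concern.** Ongoing theta and alpha power drifts from trial to trial whatever the coil does. Differencing against arrhythmic trials removes what is stable within a participant and session. It cannot remove this drift, because the arrhythmic mean comes from other trials and brings its own drift. In the compatibility effect the arrhythmic term cancels altogether: (theta − arrhythmic) − (alpha − arrhythmic) = theta − alpha.

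Because frequency is drawn at random for each trial, power before the train cannot depend on which train follows. Adjusting for it leaves the expected contrast unchanged and removes the part of the trial noise that it predicts. Without the adjustment, that noise passes into the standard deviation of the compatibility effect, which section 2.3.2 promises to report, and into the tests on spectral power.

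**Working it through.** **1. The plan's own figures.** Section 11.2 gives effect sizes and sample sizes for 95% power. Significance level and sidedness are not stated; I assume 0.05 two-sided. An exact one-sample t-test on the within-participant contrast gives:

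| Contrast | Effect size | N stated | N reproduced | Power at N = 48 |
|---|---|---|---|---|
| Theta power, theta vs arrhythmic | 0.56 | 44 | 44 | 96.7% |
| Alpha power, alpha vs arrhythmic | 0.83 | 21 | 21 | 99.99% |
| Working memory interaction | 0.532 | 48 | 48 | 95.0% |

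The sample sizes are right on their own terms. Section 11.2 gives no effect size for the site-by-frequency contrast on spectral power.

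**2. Trials per cell.** Section 6.2 gives 600 trials per session. Section 6.5.1 gives 10 blocks of 20 to 30, which is 200 to 300. If three frequencies and three cue directions are split equally (an assumption), a cell holds 600/9 ≈ 67 trials, or 200/9 ≈ 22 to 300/9 ≈ 33. Fewer trials per cell mean a larger s.

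**3. Variance after adjustment.** Let s be the share of the variance of a participant's contrast that is trial noise, and rho the within-cell correlation of pre-train with scored power. The documents give neither.

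- Covariate: ratio = (1 − s) + s(1 − rho²) = 1 − s·rho².
- Subtraction, if pre-train and scored variances are equal: ratio = (1 − s) + 2s(1 − rho).

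A simulation with 22, 33 and 67 trials per cell, slope estimated within participant, put the trial-noise part after covariate adjustment at about 0.93 (rho 0.3), 0.76 (rho 0.5) and 0.51 to 0.53 (rho 0.7). Theory gives 0.91, 0.75 and 0.51. At rho = 0 it was 1.00 to 1.03, the price of estimating a useless slope.

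**4. What it buys at N = 48.** Equivalent N is 48/ratio. Power uses effect size/√ratio.

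| s | rho | Ratio | Equivalent N | Theta power (0.56) | Power if effect is 0.40 (assumed) |
|---|---|---|---|---|---|
| any | 0 | 1.00 | 48 | 96.7% | 77.5% |
| 0.25 | 0.3 | 0.978 | 49 | 97.0% | 78.4% |
| 0.5 | 0.5 | 0.875 | 55 | 98.2% | 82.7% |
| 0.75 | 0.6 | 0.73 | 66 | 99.4% | 88.8% |

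Alpha stays at 99.99% or above throughout. The 0.40 column is a sensitivity case for the contrast that has no stated effect size; 0.40 is not in the documents. In the worst case, rho = 0 and s = 0.75, the 3% cost gives a ratio of 1 + 0.75 × 0.03 = 1.0225, and theta power of 96.4%.

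**5. Why not subtract.** Setting the two formulas equal to no change shows that subtraction breaks even at rho = 0.5, while the covariate never loses beyond the slope cost. At s = 0.5 and rho = 0.3, subtraction gives 0.5 + 2 × 0.5 × 0.7 = 1.20. The theta N for 95% power rises from 44 to 52, and power at 48 falls to 93.4%.

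**6. Room for the window.** Three cycles, half the six-cycle wavelet, last 3/5 = 0.6 s at 5 Hz and 3/8 = 0.375 s at 8 Hz. On the usual definition the wavelet's standard deviation is 6/(2πf), so three cycles is π standard deviations and the Gaussian weight there is exp(−π²/2) ≈ 0.7%. Leaving 0.6 s at each end of a 5 s gap leaves 5 − 1.2 = 3.8 s.

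**The case against.** The strongest reply is that nothing here is a defect. The planned within-session contrast is unbiased, and at the plan's own effect sizes power is already 96.7% and 99.99%. The gain rests on two quantities that the documents do not supply, and it vanishes as rho approaches 0. All of this stands.

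Silence is also not a decision. Section 11.1 describes almost no EEG preprocessing: no sensors, epochs, artefact handling or normalisation. A reader might infer that the plan has decided to discard the pre-train signal. The text supports only the narrower statement that it does not say how a baseline is to be handled.

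Third, the documents do not say where in the trial the train falls. If it falls in the delay after the cue, the pre-train window may overlap the array or the cue, and rho could be low. This bears on the size of the gain. It does not affect validity, because frequency is still assigned at random and each contrast holds cue direction fixed.

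What remains is that a primary outcome has a recorded baseline, unaffected by assignment, with no stated use, and that using it costs almost nothing even when it does not help.

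**Conclusion.** The point holds as an avoidable loss of precision. The variance of a participant's EEG contrast could fall to between 1.00 and 0.73 of its planned value, for rho from 0 to 0.6 and s up to 0.75, all assumed. Variation between participants in the true TMS effect is not reduced. The power gain is small for theta and invisible for alpha at the stated effects. It could be material for the site-by-frequency contrast, but only if that effect is smaller than the stated ones, which the documents do not tell us.

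A reader might go further and infer that the EEG analysis is underpowered, that 48 is the wrong number, or that the contrast is biased. None of these follows: the sample sizes reproduce exactly, power at the stated effects exceeds 95%, and randomisation by trial protects the unadjusted contrast as well as the adjusted one.

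**What to change.** In section 11.1, specify that within each participant and session, and for the cue direction analysed at that site, trial-level band power (preferably on the log scale) is regressed on TMS type, with the same trial's pre-train power as a covariate in the same band, sensors and scale. Carry the adjusted cell means into the arrhythmic differences, the ANOVA and the compatibility effect. Do not subtract the baseline.

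Fix one pre-train window before analysis. It should end at least three wavelet cycles before the first pulse (0.6 s at 5 Hz) and start clear of the previous train. A Morlet wavelet has no hard edge, so this makes leakage from the train negligible, not zero. State where in the trial the train falls, so that the window's overlap with the array and cue is known.

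Reconcile the trial counts in sections 6.2 and 6.5.1, since they determine how much trial noise there is.

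The cost is a short addition to the text and a little analysis work, with no new data, visits or participants. The downside is one more window to prespecify and, if rho is near 0, up to about 3% on the trial-noise part of the variance.

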6.5 COGNITIVE TASKS

6.5.1 COGNITIVE CONTROL TASK

The cognitive control task used in this paradigm consists of the presentation of colored squares on the left and right side of a computer screen. Stimuli are presented briefly, followed by a brief delay. After this, an arrow pointing to the left, right, or both left and right will briefly appear on the screen. This informs the participants which set of squares (left or right) they must remember and will be tested on. The cue is followed by another delay, and finally a new set of squares is presented. Participants press a button to indicate whether the squares are the same or different from the ones they originally saw. Between presentation of stimuli there is a small centrally presented fixation cross upon which participant maintain their gaze. Participants will complete 10 blocks of the task, each composed of 20-30 trials each. Participants will have a self-paced break between each of the blocks.

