11.2 SAMPLE SIZE DETERMINATION

Based on a previous study with the current behavioral paradigm and similar TMS manipulation, the effect size of the interaction between TMS site and TMS frequency on WM capacity was 0.532 and used 21 participants. A power analysis of this effect suggests that to reach 95% statistical power we would need to recruit 48 participants. Therefore, we will run our final analysis on 48 participants. Previous studies using a similar methodology of concurrent rhythmic TMS and EEG to look for changes in oscillatory power of the frequency of rhythmic TMS have used 10 participants for alpha frequency TMS (Thut et al., 2011) and 17 participants for theta rhythmic TMS (Albouy et al. 2017). Here, we propose to collect 48 participants. Therefore, our statistical power exceeds that of previous studies published in high-impact journals using a nearly identical methodology. Furthermore, we utilize a repeated-measures inter-mixed design in order to maximize our ability to control for confounding variables and increase statistical power. Based on a previous study by Thut et al., 2011 that found an increase in alpha oscillatory power from alpha rhythmic TMS relative to arrhythmic TMS with an effect size of 0.83 and 10 participants, we would need 21 participants to reach 95% statistical power for this comparison. Based on a previous study by Albouy et al., 2017 that found an increase in theta oscillatory power from theta rhythmic TMS relative to arrhythmic TMS with an effect size of 0.56 and 17 participants, we would need 44 participants to reach 95% statistical power for this comparison. Therefore, we estimate that based on these previously reported effect sizes for the impact of rhythmic TMS on behavior and oscillatory power measured by EEG in similar studies and our proposed sample size of 48 participants, we conclude that the proposed study has sufficient statistical power to answer the posed hypotheses.

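### Section 11.1 scores spectral power on one cue per site, which leaves the other stimulated trials out of every described entrainment estimate and makes the hypothesized frequency-by-cue interaction inseparable from frequency by site

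*Combined protocol and SAP*

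**What the plan says.** The spectral power paragraph of section 11.1 makes three predictions. Two concern entrainment against the arrhythmic control: "We hypothesize that the amplitude of theta activity will be increased following theta rhythmic TMS relative to theta activity following arrhythmic TMS", and likewise that "alpha amplitude will be increased following alpha rhythmic TMS relative to alpha amplitude following arrhythmic TMS". Neither names a cue. The third, which closes the paragraph, is an interaction between TMS frequency and cue.

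Between them stands the scoring rule: "The direction of the retro-cue is held consistent for each site: for TMS to frontal cortex (anterior-MFG) the retro-cue to the right is used". For parietal TMS the left cue is used.

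Section 6.5.1 describes three cue types: "an arrow pointing to the left, right, or both left and right will briefly appear on the screen". It does not give their proportions. Section 6.2 says that "the rhythmic TMS trains are delivered on every trial of the task".

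Section 11.2 sizes the two entrainment comparisons separately. For theta it cites an "increase in theta oscillatory power from theta rhythmic TMS relative to arrhythmic TMS with an effect size of 0.56 and 17 participants", which leads to 44 participants for 95% power. For alpha the effect size is 0.83, which leads to 21. Cue is not mentioned in either case.

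Section 2.3.2 defines a different quantity, the compatibility effect: theta against alpha TMS, with right cues for the frontal site and left cues for the parietal site. It gives a reason: frontal theta arises when the cue is to the contralateral field, and parietal alpha when it is to the ipsilateral field.

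**The concern.** The cue restriction suits the compatibility effect of section 2.3.2, which is defined by cue. The entrainment comparisons are different contrasts (rhythmic minus arrhythmic) and are stated and sized without a cue. Applied to them, the restriction sets aside trials that were stimulated and recorded and that bear on the question.

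It also undercuts the third prediction. If each site contributes one cue only, no comparison between cues is possible within a site, and any difference between cues is also a difference between sites.

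At stake is the check that the stimulation did what it was meant to do. If the entrainment estimate is weak, a null compatibility effect is hard to read, because failed entrainment and noisy measurement look alike. Without a pre-specified all-cue analysis, the choice between one-cue and all-cue entrainment results could also be made after seeing the data.

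**Working it through.** **1. Confounding.** Site by cue cells used for spectral power under section 11.1:

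| Site | Left | Right | Both |
|---|---|---|---|
| anterior-MFG | not used | used | not used |
| inferior-IPS | used | not used | not used |

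Two of six cells are filled, and cue is determined by site. A frequency-by-cue term is therefore the same column as frequency by site. The trial design itself does not force this; the scoring rule does.

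**2. Share of trials left out.** Let q be the share of two-sided cues, with left and right equally frequent (neither is stated). The share used is (1 − q)/2, and the share left out is 1 − (1 − q)/2.

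- q = 0: 50%
- q = 0.2: 60%
- q = 1/3: 66.7%
- q = 0.5: 75%

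Trials per session are given inconsistently: 600 (section 6.2), 2400 pulses / 5 per train = 480 (section 6.2), and 10 blocks of 20 to 30 = 200 to 300 (section 6.5.1). With equal frequencies and equal cues, the trials per frequency (total/3) and on the analysed cue (total/9) are:

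| Total | Per frequency | Analysed cue |
|---|---|---|
| 600 | 200 | 67 |
| 480 | 160 | 53 |
| 300 | 100 | 33 |
| 200 | 67 | 22 |

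**3. The plan's own sample sizes.** Paired t-test, exact noncentral t, two-sided 5% (assumed, as the plan does not state it), 95% power: effect size 0.56 needs 44, 0.83 needs 21 and 0.532 needs 48. All three match section 11.2. At 48 participants, power is 96.7% for 0.56 and above 99.9% for 0.83.

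**4. Gain if the effect sizes describe a one-cue contrast.** Let f be the share of a participant's one-cue contrast variance that is trial noise (not in the documents). Assume equal cue shares, the same entrainment at every cue, and a between-person part common to all cues. Using all trials multiplies the SE by √(1 − f + f/3).

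| f | SE multiplier | Theta effect size | Theta power, N = 48 |
|---|---|---|---|
| 0 | 1.00 | 0.560 | 96.7% |
| 0.5 | 0.82 | 0.686 | 99.6% |
| 1 | 0.58 | 0.970 | >99.9% |

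**5. Loss if the effect sizes describe an all-trial contrast.** Now f is the trial-noise share of the all-trial variance. One-cue scoring divides the effect size by √(1 − f + 3f).

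| f | Theta: effect size, power | Alpha: effect size, power |
|---|---|---|
| 0 | 0.560, 96.7% | 0.830, >99.9% |
| 0.5 | 0.396, 76.6% | 0.587, 97.8% |
| 1 | 0.323, 59.3% | 0.479, 90.2% |

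**6. Unequal entrainment.** If the other cues entrain at a fraction r of the analysed cue, the cue average has effect size d(1 + 2r)/3 ÷ √(1 − f + f/3). It beats the single cue only if r exceeds (3√(1 − f + f/3) − 1)/2, which is 87%, 73% and 56% for f = 0.25, 0.5 and 0.75. As an illustration, take d = 0.40 on the analysed cue (an assumed value, 77% power at N = 48) and r = 62.5%. The effect sizes become 0.329, 0.367 and 0.424, with power 61%, 70% and 82%. Averaging loses in two of the three cases.

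**The case against.** The strongest reply is that the restriction is deliberate. Section 2.3.2 explains why theta and alpha are expected under particular cues, and the spectral power paragraph of section 11.1 itself predicts that frequency effects depend on cue. Looking where the effect is expected is a reasoned choice, and step 6 shows that averaging over cues can cost power. This stands. It is why the compatibility effect should be left alone and why a cue average must not be reported by itself. It does not rescue the cue interaction, which one cue per site cannot test.

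It can also be said that the cue sentence is repeated for all three outcomes and is not expressly tied to the entrainment comparisons. That is fair, but no other trial set is described for them.

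A reader might go further in four ways that the documents do not support:

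- That two-thirds of trials are lost. This needs equal cue shares, which are not stated.
- That the data are discarded. They are unused in this score; nothing says they are excluded from every analysis.
- That entrainment must be equal across cues because the two hypotheses name none. Silence is not equality, and the same paragraph predicts an interaction.
- That the study is therefore underpowered. If 0.56 and 0.83 describe one-cue contrasts, power at 48 participants is already 97% or more.

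**Conclusion.** The point holds as an inconsistency between hypotheses and scoring. The confounding of cue with site is certain from the text and needs no assumption. That no described entrainment estimate uses the remaining trials also follows from the text as written. Their share is 50% to 75% if left and right cues are equally frequent and two-sided cues make up at most half.

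The effect on precision is not determined. It runs from nothing to a substantial loss, depending on the trial-noise share, on whether entrainment is similar across cues, and on which contrast the cited effect sizes describe. Section 11.2 does not settle the last of these. The case for change rests on making the stated hypotheses testable with data already planned, not on a demonstrated power shortfall. It is a worthwhile, inexpensive improvement.

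**What to change.** In section 11.1:

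- Leave the cue-specific compatibility effect of section 2.3.2 unchanged.
- For spectral power, pre-specify the rhythmic-minus-arrhythmic entrainment comparisons (theta and alpha, at each site) on all trials, with cue (left, right, both) as a factor.
- Report the cue-average estimate, the per-cue estimates and the frequency-by-cue interaction together.
- State the planned proportions of the three cue types, and say in section 11.2 whether the effect sizes are taken to describe one-cue or all-trial contrasts.

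The differing trial counts in sections 6.2 and 6.5.1 must be reconciled so that the number of trials per condition is known.

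The cost is SAP wording and some analysis work; no new data are needed. The downside is dilution: if entrainment is weaker on the other cues, as the plan's own cue hypothesis allows, the cue average is smaller and can have less power than the single-cue estimate. The per-cue estimates must therefore always stand beside it.
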